Warning: Save your work at least every 15 minutes by clicking "Save" or "Continue."

Lay Summary and Keywords

Please provide the following information about your study.

1.0 *Provide a brief lay summary describing this study. (limit 500 words).

This study is designed to conduct a double-blind placebo-controlled trial of Namenda (Memantine) as an augmentation to Lexapro (Escitalopram) in depressed older adults 60 years of age and older with mild cognitive impairment. Throughout the course of the study, we anticipate screening about 400 subjects to recruit 134 participants in the first four years. This study will require that the subjects complete up to 20 (twenty) visits in 12 (twelve) months to the study site during their participation.

The purpose of this study is to determine whether Namenda® (memantine) when taken in combination with Lexapro® (escitalopram), may improve the quality of treatment response by making it faster and more complete, and also by improving thinking and memory in comparison to Lexapro taken with a placebo. Enrolled subjects will be provided with 10-20 mg of escitalopram for 12 months, and concurrently randomly assigned to either memantine or placebo groups. We will also examine the safety and tolerability (how well the treatment works and the side effects) of a combination of Namenda and Lexapro as compared to placebo and Lexapro in subjects with major depressive disorder and mild cognitive impairment who are at least 60 years of age. Individually, Namenda and Lexapro have been tested for safety and efficacy in younger and older adults and are approved by the United States Food and Drug Administration (FDA) for use in human subjects, including people older than 60 years old. However, the combination of Namenda and Lexapro for the treatment of depression with mild cognitive impairment is experimental and different from the FDA approved use for each drug. Namenda is not FDA approved for depression in any age group.

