The proposed project will also evaluate the role of neuroimaging biomarkers of brain aging (i.e., neurodegenerative and vascular brain changes) and mild cognitive impairment in the patterns of treatment response to memantine combined with escitalopram compared to escitalopram and placebo. Memantine is likely to accelerate and enhance antidepressant response to escitalopram and improve cognitive performance. Subjects with amnesic mild cognitive impairment or biomarkers of brain aging at baseline are likely to have preferential response to the combination of memantine and escitalopram compared to escitalopram and placebo.

We will conduct neuroimaging using two functional and structural magnetic resonance imaging (MRI) scans and a positron emission tomography (PET) scan. The purpose of the imaging procedure is to measure the amyloid and tau protein in the brain using the identified substance called [18F]FDDNP to predict the response to depression and memory treatments.

Additionally, we will explore the levels of telomerase and NFkappaB as correlates of depression as predictors of response to the interventions directed toward improvement in the severity of depression, quality of life and resilience. We will examine the role of 2 candidate genes involved in the regulation of mood and memory, and evaluate telomerase and NFkappaB activity before and after the intervention. This proposal is a continuation of our ongoing work in this area.

2.0 ***List three to five keywords describing this study (separate the words with commas). The keywords may be used for identifying certain types of studies.**

geriatric depression, MCI, neuroimaging, biomarkers, memantine

3.0 *** Is this study conducted or supported by HHS (e.g., the National Institutes of Health, Centers for Control and Prevention, etc.)?**

Yes No

3.1 *** Is NIH the HHS agency supporting or conducting the study?**

Yes No

3.2 *** Please choose one:**

I acknowledge that my study is automatically covered by a Certificate of Confidentiality and I understand the responsibilities associated with that Certificate.

The NIH Certificate of Confidentiality policy does not apply to my study (see guidance at right and explain below)

4.0 *** Is this study regulated by the Food and Drug Administration (FDA)?**

Yes No

4.1 **If yes, check all that apply:**

Human Drugs

Medical Devices

Biological Products

Mobile Medical Applications

Food Additives

Color Additives

Other

ID: IRB#12-001714

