Specific Aim 1. To compare the quality of treatment response in older depressed subjects to escitalopram+placebo (esCIT+PBO) vs. escitalopram+memantine (esCIT+MEM) in a 6 month acute treatment trial with 12 month follow up.

Hypothesis 1. Improved levels of depression and cognition will be observed in depressed subjects treated with combined escitalopram+memantine compared to those treated with escitalopram+placebo.

Specific Aim 2. To determine the role of a) brain pathology (MRI and FDDNP-PET measures) and b) MCI diagnosis in predicting and moderating antidepressant response to study drugs in depressed subjects.

Hypothesis 2a. Measures of brain pathology (volume and localization of white matter hyperintensities, regional gray and white matter volumes, hippocampal atrophy, functional brain connectivity using cognitive task activation, FDDNP-PET binding levels) will predict and moderate antidepressant response to escitalopram and memantine or escitalopram and placebo in: 1) rate of remission; 2) rate of depression relapse; and 3) improvement in cognitive performance.

Hypothesis 2b. MCI diagnosis will predict and moderate preferential antidepressant response to escitalopram and memantine.

Aim 3: To test whether the two treatment conditions can improve neurocognitive performance and working memory function surveyed with task-related fMRI at 12 weeks and/or during the 6 months follow-up. Hypothesis 3a: Compared to escitalopram+PBO, escitalopram+MEM will improve cognitive performance on tests of a) memory after 12week treatment and at 6 months follow-up. Hypothesis3b: Likewise, escitalopram+MEM will increase working memory-related activation of dorso-lateral prefrontal cortex (DLPFC)

Aim 4. To determine whether both structural and functional brain imaging markers will predict and/or moderate antidepressant response in both treatment conditions.

Hypothesis 4: Imaging biomarkers will moderate and predict 1) rate of remission; 2) rate of depression relapse and recurrence; and 3) improvement in cognitive performance.

Exploratory hypothesis 1: We will explore the relationship of apolipoprotein E-4 allele (APOE-4) to [18F]FDDNP PET binding in subjects with DEP+MCI. We expect that APOE-4 allele carriers will have higher FDDNP binding in the medial temporal lobe compared to non-carriers, and will experience greater cognitive decline on neuropsychological tests and fMRI memory tests.

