In addition, this is the first trial combining memantine and escitalopram for the treatment of late-life depression (with/without a-MCI) that integrates brain aging biomarkers of cerebrovascular and neurodegenerative changes that focuses on predictors and moderators of treatment response. Stratification by higher risk group for brain aging (i.e., a-MCI; late-onset) has important implications for identifying high-risk subgroups of elderly depressed subjects with preferential response to the combination of an antidepressant and cognitive enhancer that creates a potent “mood+cognitive enhancer,” which acts via glutamatergic and serotonergic neurotransmission. This combination should theoretically have greater efficacy and a more rapid response compared to an SSRI, especially in those with a-MCI and brain aging. Finally, in addition to assessing primary outcomes, we will explore the benefits of each treatment option on resilience, health-related quality of life, and life satisfaction during 12-month follow up. If our hypotheses are correct, this approach will inform clinical practice to use memantine to enhance antidepressant response and maintain such improvements in older adults with major depression and MCI, especially in those with additional biomarkers of brain aging (cortical atrophy, WMH, [F-18] FDDNP binding), thus developing personalized approaches to the treatment of geriatric depression. Future directions of this work will include developing specific interventions targeting biomarkers of brain aging in geriatric depression and the development of preventive interventions for depression relapse and recurrence in older adults, as well as prevention or delay of conversion to dementia in high risk groups.

C. Background and Rationale. 1. Overview. Despite progress in antidepressant therapies, a considerable number of depressed elderly patients develop either a chronic condition or relapse frequently after periods of improvement 58-61. Elderly patients appear to have a particularly brittle response with a higher rate of recurrence and a shorter interval before recurrence.62,63 Cognitive impairment has been implicated in inadequate treatment response 412. Clinical features of geriatric depression. Geriatric depression is associated with greater medical and cognitive comorbidity, structural brain changes, and higher rates of apathy, anxiety, and suicide, as well as poorer treatment response compared to younger adults 41,64-70.

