Hypothesis 2b. We will also perform categorical data modeling in a 2 (MCI present/absent) x 2 (treatment group) x 2 (response: remitter/non-remitter) table. Randomized stratification by MCI will ensure balanced ratio of subjects with MCI across treatment groups. We will use the Grizzle, Starmer, Koch (1969) approach to linear modeling as implemented in SAS PROC CATMOD. The hypothesis that there is a MCI effect only in the esCIT+MEM condition is tested by the cognition x drug interaction term. Subsequent linear contrasts will compare cognitive groups within treatment groups. The test of MCI on cognitive domain scores will use an analysis paralleling the analysis of treatment effects noted above (mixed effects model with cognitive domain serving as a repeated measure), but with MCI and treatment defining groups. We anticipate that there will be a main effect of MCI associated with poorer baseline performance, but also a main effect of MCI on change (as indicated by a treatment x MCI) interaction effect. Similar analyses, replacing MCI present/absent by early/late onset, will be performed with age of onset. Significance of the treatment x onset interaction effect will allow us to determine if early or late onset is associated with improved performance.

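### Hypothesis 2b follows a valid interaction test with MCI-versus-no-MCI contrasts inside each arm, and never specifies the memantine-versus-placebo estimate within MCI that its question calls for

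*Combined protocol and SAP*

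**What the plan says.** **The question.** Section 10.1, item 2.0 states Hypothesis 2b as: "MCI diagnosis will predict and moderate preferential antidepressant response to escitalopram and memantine". The lay summary (section 2.2) says that patients with amnestic MCI or imaging markers of brain aging "are likely to have preferential response to the combination of memantine and escitalopram compared to escitalopram and placebo". The Innovation text in item 3.0 adds that, if the hypotheses are right, "this approach will inform clinical practice to use memantine to enhance antidepressant response and maintain such improvements in older adults with major depression and MCI". All three concern memantine against placebo: its effect in patients with MCI, and whether that effect is larger than in patients without MCI.

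**The analysis.** Item 6.0 models a "2 (MCI present/absent) x 2 (treatment group) x 2 (response: remitter/non-remitter) table". It continues: "The hypothesis that there is a MCI effect only in the esCIT+MEM condition is tested by the cognition x drug interaction term". The next sentence is: "Subsequent linear contrasts will compare cognitive groups within treatment groups". The same scheme is then applied to early versus late onset. For cognitive scores, a mixed model uses MCI and treatment as grouping factors, again with no arm contrast within MCI named.

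**The sample.** Item 4.0 randomises 1:1, stratified by a-MCI status and onset. The inclusion criteria (section 11.1, item 4.0) do not require MCI, and the background expects about 50% with a-MCI (46% in the pilot samples).

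**The concern.** Two things are wrong.

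First, the follow-up contrasts run in the wrong direction. MCI status is not randomised, so a difference between patients with and without MCI inside one arm reflects prognosis as well as any drug effect. Treatment is randomised, and within a-MCI strata, so the arm comparison inside a stratum is the one protected by the design. That comparison is not specified for any outcome under Hypothesis 2b. Hypothesis 1 does not stand in for it, because it averages over patients with and without MCI.

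Second, the pattern sought, an MCI effect in the memantine arm only, is one way in which preferential benefit can appear, but not the only one. The background says: "Cognitive impairment has been implicated in inadequate treatment response". If that applies to escitalopram plus placebo, a drug that helps MCI patients more would narrow an existing deficit. The table would then show a deficit on placebo and little or no MCI effect on memantine.

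What is at stake is interpretation. A reader following the named contrasts could miss a real benefit in MCI. Any recommendation for MCI patients would then rest on an estimate chosen after the data were seen.

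**Working it through.** **The plan's own figure.** Item 6.0 assumes 134 randomised (67 per arm), 25% dropout, 50 completers per arm, 70% versus 40% remission and a two-sided 0.05 chi-square test. It states power above 80%.

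- z = [0.30 − 1.96 × √(2 × 0.55 × 0.45 / 50)] / √[(0.70 × 0.30 + 0.40 × 0.60) / 50] = (0.300 − 0.195) / 0.0949 = 1.107, so power is 0.866.
- With continuity correction it is 0.815. The stated figure reproduces. No power is given for Hypothesis 2b.

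**Cell sizes.** At 50% a-MCI: 50 × 0.5 = 25 completers per cell, or 67 × 0.5 = 33.5, taken as 33, if all randomised patients count.

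**What the planned contrasts show.** The remission rates below are assumed, in percent. MEM is escitalopram plus memantine and PBO is escitalopram plus placebo. Interaction = (MEM MCI − MEM no MCI) − (PBO MCI − PBO no MCI). The overall difference assumes half the sample has MCI.

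| Scenario | MEM: MCI / no MCI | PBO: MCI / no MCI | Overall MEM − PBO | Interaction | MCI effect in MEM | MCI effect in PBO | MEM − PBO in MCI | MEM − PBO, no MCI |
|---|---|---|---|---|---|---|---|---|
| 1 | 85 / 55 | 40 / 40 | +30 | +30 | +30 | 0 | +45 | +15 |
| 2 | 70 / 70 | 25 / 55 | +30 | +30 | 0 | −30 | +45 | +15 |
| 3 | 70 / 40 | 70 / 70 | −15 | +30 | +30 | 0 | 0 | −30 |
| 4 | 40 / 60 | 40 / 40 | +10 | −20 | −20 | 0 | 0 | +20 |

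Scenarios 1 and 2 both average to the plan's 70% and 40%. They share the overall effect, the interaction and the benefit in MCI. Only the planned contrasts differ: the sought pattern is present in 1 and absent in 2. Scenarios 1 and 3 share both planned contrasts and the interaction, but memantine adds 45 points in MCI in one and nothing in the other.

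**Power at 25 per cell.**

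- Scenario 2, MCI versus no MCI within memantine: 5%, the null level, since the true difference is zero.
- Scenario 2, memantine versus placebo within MCI (70% versus 25%): z = [0.45 − 1.96 × √(2 × 0.475 × 0.525 / 25)] / √[(0.21 + 0.1875) / 25] = (0.450 − 0.277) / 0.126 = 1.373, power about 0.915.
- Interaction, scenarios 1 and 2: SE = √(0.855 / 25) = 0.185, power 0.37. With 33 per cell: SE 0.161, power 0.46.

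**Precision of the missing estimate at 70% versus 40%.** Half-width = 1.96 × √[(0.21 + 0.24) / n].

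- n = 25: 1.96 × 0.134 = 0.263, interval about 4 to 56 points, power 0.57.
- n = 33: 1.96 × 0.117 = 0.229, interval about 7 to 53 points, power 0.70.

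**The case against.** The strongest reply is that Hypothesis 2b is about moderation, and the interaction is the right test for it. The interaction is the difference between two randomised treatment effects, and it is the same number whichever way the table is read. That stands. A reader might infer that the plan cannot estimate the effect in MCI at all. The documents do not support this: the planned table holds all four proportions, and with equal strata the within-MCI effect equals the overall difference plus half the interaction (30 + 15 = 45 in scenarios 1 and 2). The gap is in what is specified and reported.

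A reader might also infer that a benefit confined to patients without MCI would look like the prediction, as in scenario 4. That needs the sign to be ignored. The documents predict better response in MCI, whereas scenario 4 shows −20 within memantine and an interaction of −20. Scenario 3 has the right sign but needs memantine to harm patients without MCI by 30 points. Hypothesis 1 would expose it, with −15 overall against +30 in scenario 1.

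A third tempting reading is that the sought pattern contradicts the protocol's own account of prognosis. That account is one hedged sentence. The protocol's figures show no clear deficit on an SSRI alone: 30.7% remission among pilot completers on escitalopram, who had MCI, against about 30% quoted for older depressed patients generally. The comparison is rough, but it makes the authors' pattern a coherent possibility. It does not make that pattern equivalent to preferential benefit.

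Finally, the lay summary describes participants as "in depressed older adults 60 years of age and older with mild cognitive impairment". If all had MCI, Hypothesis 1 would answer the question. The inclusion criteria, the expected 50% and the MCI-absent level of the planned table show a mixed sample.

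**Conclusion.** The point holds as a fault in the follow-up to Hypothesis 2b, and no further. The interaction test is sound, and the primary comparison and its sample size are unaffected. The contrasts named after the interaction are non-randomised and answer a different question from the one in the aims. The within-MCI treatment estimate is available from the planned table but is not specified. Under the assumed rates of scenario 2, which keep the plan's 70% and 40%, a 45-point benefit in MCI coexists with a zero MCI effect in the memantine arm.

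This rests on illustrative cell rates, a 50% share with a-MCI and equal dropout across cells. The documents also leave the stratum unclear: randomisation uses a-MCI, while the Hypothesis 2b table uses MCI present or absent, which is broader. The cell sizes above are for a-MCI.

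**What to change.** In section 10.1, item 6.0, Hypothesis 2b:

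- Replace the within-arm cognitive contrasts with escitalopram plus memantine versus escitalopram plus placebo within each cognitive stratum, and likewise within each onset stratum. Report risk differences with 95% confidence intervals beside the interaction estimate.
- Define the cognitive stratum as a-MCI status, the randomisation stratum, or state explicitly that the broader MCI definition is used.
- Restate the hypothesis as: the memantine-minus-placebo difference in remission is larger in patients with MCI than in those without.
- Keep MCI versus no MCI within arm as a description of prognosis only.

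The cost is a few lines of text and contrast statements in the model already planned, with no new data or visits. It should be done before treatment codes are opened. The price is candour about precision: the within-MCI interval of about ±26 points (25 per arm) or ±23 points (33 per arm) must be reported as it is, and a non-significant result must not be read as absence of benefit.

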7) **Follow up assessment:** The follow up will take place weekly for the first 4 weeks of treatment and every 2 weeks for the remaining 5 months of the 6 months trial, followed by naturalistic follow up monthly up to 12 months. Each follow up assessment will include measures of efficacy and safety. The need for repeated assessments stems from our hypothesis of difference in time-to-remission occurring during the extension treatment. The weekly frequency of contact with all subjects will serve as an additional safeguard to monitor worsening of depression, as well as the emergence of side-effects or suicidal ideations. All assessment procedures described below are identical for the two groups. Most of the instruments have been administered in our ongoing studies, and our subjects age 60 and older tolerate their administration quite well (Table 2).

Primary outcomes will be measured and defined as follows: 1) Remission will be defined as HAM-D scores of 6 or less for 3 consecutive weeks, week 12 and at 6 months visit; 2) Depressive relapse is defined as an episode of major depressive disorder that occurs within 6 months after remission, while 3) recurrence is defined as another depressive episode that

occurs after 6 months have elapsed.

Assessment and monitoring of suicidal risk will occur at each visit and by phone between visits. We have applied the standard procedures that are required and approved by the UCLA Institutional Review Board. We have employed the same procedures in our ongoing studies of late-life depression since 1995, and have had no suicide attempts among our subjects. We will monitor suicidal ideations using the 3rd item of the Hamilton Depression Scale during each visit to the site and the Beck Scale of Suicidal Ideations (SSI). Monitoring for SI will be done at each visit independent of the outcome assessment.

Monitoring of expectations for symptomatic improvement: Since subjects will enter the treatment process for symptomatic improvement, we will account for a differences in expectations between the two groups. Thus, subjects' expectations for improvement will be assessed during the baseline visit, at week 12, at the end of the acute treatment trial (Week 24), and during follow up. We will control for any differences in the analyses.

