Data Analysis. Primary analyses will be carried out on an intent-to-treat basis; additional analyses considering dropout or other observable post-randomization outcomes will make use of an instrumental-variable analysis framework. Data will be examined initially to identify issues such as departures from normality, which would suggest the need for transformations (e.g., logarithmic) and influential observations (outliers). Descriptive statistics will be computed and reported overall and by group. Demographic variables and variables characterizing the course of depression (e.g., age of onset, chronicity, number of episodes) will be screened to determine which have relationships with the outcome variables that would suggest their value as covariates. Variables that demonstrate meaningful associations with outcomes controlling for treatment group and are substantially different across groups are candidates for covariates. Demographic variables, baseline depression, and other potential covariates will be compared between the two groups to help determine if the randomization was successful in making the two groups comparable. Specific analysis plan follows below.

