Hypothesis 1. The primary outcome, namely responder/remitter status, will be compared between the esCIT+MEM and esCIT+PBO groups using chi-square statistics. Days to remission will be analyzed using the Kaplan-Meier survival method with treatment group as a stratification variable using the day on which response was observed as the event indicator. The survival function estimates the proportions achieving the response criterion, while the overall survival curve reflects speed of response. The independent variable is treatment group with two levels. A log-rank test will be used to assess the significance of any difference between treatment arms, and Cox regression to reflect the role of baseline covariates. We will also report the total time spent below the response threshold, compare summary statistics, and patterns of response within the patient over time. Analysis of change over time will be performed using linear mixed model analysis of covariance (SAS PROC MIXED). The linear mixed model permits flexible specification of the covariance structure of the repeated measures within patient, and allows analysis of incomplete cases using maximum likelihood. The outcome measures will be the HAM-D scores as well as cognitive domain scores (i.e. memory, processing speed, executive function) with the baseline rating/score on each domain as a covariate.

Hypothesis 2a. The role of brain neuroimaging biomarkers in variability of treatment response is examined in this Hypothesis. Predictor variables: We predict that baseline measures of neuroimaging biomarkers (white matter hyperintensity, regional gray or white matter volumes, hippocampal thickness and regional FDDNP binding levels) will be related to treatment outcomes. These predictions will be evaluated in the context of the models described above (i.e., general linear mixed model) by adding the posited prognostic variable as an additional predictor. Moderator variables: A limited number of exploratory analyses will be performed to evaluate possible moderators of each treatment strategy. Statistical evaluation of moderators will be done by including the posited moderator variable as an independent variable and evaluating the moderator x treatment group interaction term. Mediator Variables: We will evaluate the variable as a potential

mediator using a principal stratification framework.17,20

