Power analysis. The power analysis is focused on the primary aim of the study to assess whether the group receiving combined MEM and escitalopram demonstrate remission (HAM-D<6) compared to the other group. In the PI's pilot data, we observed remission in 83.3% of patients receiving the combination esCIT+MEM, compared to 30.7% in those receiving esCIT+PBO. In line with the message of Kraemer, et al. (2006) emphasizing that it is not safe to ignore uncertainty in pilot-study estimates of effect size, which risks underpowering the subsequent study, we derive a sample size appropriate to an effect considerably smaller than the observed difference. Specifically, we work with an assumption that the remission rate in the esCIT+MEM arm would be 70% (smaller than the observed rate of 83.3%) and that the remission rate in the esCIT+PBO arm would be 40% (larger than the observed rate of 30.7%). More involved analyses would be possible that average over a range of scenarios; the approach used here captures the essential feature that it is important to allow for possible regression to group means that are less different than those observed in the pilot study. We will draw on frameworks from the Institute of Medicine report on avoiding missing data,²² but if we recruit a total of 134 patients (67 per group) with a projected 25% dropout rate, we will be able to compare 50 completers in the esCIT+MEM group with 50 subjects in the esCIT+PBO group. Assuming that 70% of the group receiving esCIT+MEM respond versus 40% of the control subjects, the power for this chi-square test, at the 0.05 level of significance with 1 degree of freedom, exceeds 80%. To assess the impact of the proposed sample size on other analyses, we also investigated a repeated-measures analysis of our pilot data with continuous HAM-D scores as an outcome, comparing the treatment groups at 24 weeks, using the baseline measure as a covariate. We found that the effects observed in the pilot data (but reassessing with the proposed sample size) yielded a power over 0.9. In addition, we will compare the groups on the number of days until response using survival analysis. If we combine the groups and assume 40% dropout, the power of the two-sided log rank test at the 0.05 level of significance will be 0.869 with the proposed sample size.

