All severe adverse events will be reported to the subjects and to their primary physicians and the UCLA IRB/ DSMB committee within 1 week of the PI's awareness, and within 2 weeks to the NIH.

- d. If a patient demonstrates worsening of their symptoms or no response by week 8 (i.e., less than 30% improvement in HAM-D scores or CGI score of > 4) of treatment, they will be discontinued from the study and referred for appropriate clinical services.
- e. The allowed dose range for MEM will be 5-20 mg/day; escitalopram 10-20 mg/day. If patients are not able to tolerate these medications, they will be discontinued from the trial.
- f. Suicidal ideations with the HAM-D item 3 score of 3 and greater, or worsening of the score on the Beck Suicidal Ideation scale.

All dropouts will be analyzed by the reason for termination and classified as: 1. Reasons: a) Lack of efficacy; b) Side-effects; c) Lost-to-follow up; d) Hospitalization; e) Death; f) Other
2. Relation to the study drug use: a) likely; b) probable; c) unlikely.

Structural and Functional Magnetic Resonance Imaging (s- and f-MRI) Scan. The risks or discomforts associated with MRI scans may include anxiety from being in a tight, enclosed space, or discomfort from staying still for too long. Should you become anxious or agitated during the MRI scan, this research study will be immediately discontinued. The sound of the MRI scanner can be loud. We will provide earplugs to minimize the noise, but some people find the noise annoying. The tests themselves can be boring or difficult, and you may get fatigued during the scan or from the diagnostic tests.

Occasionally subjects report having a headache, feeling stiff, or feeling anxious from claustrophobia after the scan.

The magnetism of the machine attracts certain metals; therefore, people with metals in them (specifically, pacemakers, infusion pumps, aneurysm clips, metal prostheses, joints, rods, or plates) will be excluded from the study. The "metal" in dental fillings is less susceptible to magnetism and is therefore allowed. The participant will be asked about any potential sources of metal, and you pockets will be emptied prior to the study. The participant may wish to stop the study at any stage, including the testing stage. Testing will last less than 15 minutes.

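### Power is computed for 50 v 50 completers, but the primary analysis is intent-to-treat with no rule for counting dropouts in the chi-square; a 24-week power figure is also credited to a 12-week pilot

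*Combined protocol and SAP*

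**What the plan says.** Section 10.1 item 6.0, Data Analysis: "Primary analyses will be carried out on an intent-to-treat basis". Hypothesis 1 in the same item makes the primary test a chi-square on responder/remitter status. The Power analysis paragraph takes 67 per group, projects 25% dropout and states that "we will be able to compare 50 completers in the esCIT+MEM group with 50 subjects in the esCIT+PBO group", with power above 80% at 70% v 40%.

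Dropout or incomplete data come up in five places:

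- Data Analysis: "additional analyses considering dropout or other observable post-randomization outcomes will make use of an instrumental-variable analysis framework". This covers additional analyses only.
- Hypothesis 1: the linear mixed model "allows analysis of incomplete cases using maximum likelihood". This covers continuous scores only.
- Power analysis: a pointer to frameworks for avoiding missing data.
- Sections 14.1 item 3.0 and 15.2 item 5.1: "All dropouts will be analyzed by the reason for termination and classified as", followed by a list of reasons and of relation to study drug, with no outcome status.
- Section 10.1 item 4.0, naturalistic follow-up: patients who do not remit are offered treatment outside the protocol and invited to the 6- and 12-month visits. How those visits count is not said.

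On timing, discontinuation criterion d in 14.1 and 15.2 reads "If a patient demonstrates worsening of their symptoms or no response by week 8", and such patients leave the study. Section 10.1 item 4.0 says: "Remission will be defined as HAM-D scores of 6 or less for 3 consecutive weeks, week 12 and at 6 months visit". Hypothesis 1 adds: "Days to remission will be analyzed using the Kaplan-Meier survival method".

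**The concern.** A chi-square needs a yes or no for every patient analysed. Intent-to-treat fixes who is analysed. It does not fix what value a missing outcome takes. About a quarter of the patients are expected to leave, and the power text is written as if they were set aside. Excluding them, imputing them and counting them as non-remitters are different primary analyses, and nothing stops the choice being made after the data are seen.

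The choice is not neutral. The week-8 criterion removes patients because they are doing badly, before the endpoint can be assessed. A comparison of those who stay is selected on outcome. Censoring the withdrawn patients in the Kaplan-Meier analysis treats them as if they were as likely to remit later as those who stayed.

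The stated power also belongs to a different analysis from the one called primary. Its relevance depends on whether 70/40 describe completers or everyone randomised, and the text points both ways.

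**Working it through.** **Inputs.** Power analysis: 67 per arm, 25% dropout, 70% v 40%, chi-square at 0.05 (taken as two-sided). Pilot, section 10.1 item 3.0: 14 treated per group, remission in 10 of 12 and 4 of 13 completers.

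**Formula.** With n per arm and p̄ = (p1 + p2)/2, power = Φ{[|p1 − p2| − 1.96·√(2p̄(1 − p̄)/n)] / √(p1(1 − p1)/n + p2(1 − p2)/n)}. Each result is followed by exact enumeration of the uncorrected Pearson chi-square.

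**1. The plan's own figure.** 67 × 0.75 = 50.25, so 50 per arm. At 70/40: (0.30 − 1.96 × 0.0995)/0.0949 = 1.107, giving 0.866 (exact 0.876). The claim of more than 80% is reproduced.

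**2. Intent-to-treat, 70/40 as completer rates, dropouts as non-remitters.** Expected dropouts are 67 × 0.25 = 16.75 per arm. Rates become 0.75 × 0.70 = 52.5% and 0.75 × 0.40 = 30%. At n = 67: (0.225 − 1.96 × 0.0851)/0.0828 = 0.704, giving 0.759 (exact 0.752).

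**3. Intent-to-treat, 70/40 as all-patient rates.** At n = 67: (0.30 − 1.96 × 0.0860)/0.0820 = 1.605, giving 0.946 (exact 0.941).

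**4. Unequal dropout on the completer-rate reading.** These splits are illustrations, not plan inputs; both average 25%.

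| Dropout, memantine / placebo | Rates | Power (exact) |
|---|---|---|
| 23% / 27% | 0.77 × 0.70 = 53.9% v 0.73 × 0.40 = 29.2% | 0.834 (0.828) |
| 27% / 23% | 0.73 × 0.70 = 51.1% v 0.77 × 0.40 = 30.8% | 0.670 (0.662) |

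**5. Which reading of 70/40?** The text speaks of the rate in the arm, which suggests all patients. But it sets 70% against an observed 83.3%, which is 10/12, a completer rate, and applies 70/40 to 50 per group. With pilot dropouts counted as non-remitters, the all-patient pilot rates are 10/14 = 71.4% and 4/14 = 28.6%.

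**6. Direction of the selection.** Suppose, for illustration, that true remission is 40% and the week-8 criterion removes 35% of eventual non-remitters and no remitters. Among those left the rate is 0.40/(0.40 + 0.60 × 0.65) = 50.6%. Censoring at withdrawal errs in the same direction.

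**7. The 24-week figure.** The pilot section describes 12 weeks of treatment and an effect from baseline to 12 weeks. The power paragraph reports a comparison at 24 weeks from those data, with power over 0.9. The size is plausible: a t-test at 50 per arm with the pilot's 0.76 SD gives 0.964. The time point has no source in the text. The effect used is not named, and the pilot section offers several (0.76, 1.2 and a repeated-measures F of 2.6).

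**The case against.** Four arguments on the other side carry weight.

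- The power arithmetic is right for the comparison it describes, so this is a gap in specification. That stands.
- The wording favours all-patient rates, which gives about 94%. The all-patient pilot gap of about 43 points shows that a 30-point gap is already cautious on that basis. That stands as the more natural reading of the word arm, but the completer comparator and the 50 per group keep the other reading open.
- The 25% comes from the investigators' earlier methylphenidate trials, and the text does not say whether those had a week-8 criterion. So the share of dropout driven by outcome is unknown. The criterion itself is explicit, however, and acts before remission is judged.
- A rule may sit in the grant application or assessment schedule listed as attachments in section 10.1 item 1.0, which are not in the supplied text. That cannot be excluded. The analysis section should still state it.

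A reader might infer that the trial is underpowered, or that the figure above 80% is a miscalculation. The documents support neither: about 75% needs completer rates, equal dropout and every dropout a non-remitter, while another open reading gives about 94%. A reader might also infer that the figure over 0.9 hides its reliance on raw pilot results. It does not: the text says it uses the effects seen in the pilot. Nor does the log-rank sentence's 40% dropout show an error.

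**Conclusion.** The point holds as a matter of analysis specification and power basis, and should be fixed. The primary analysis is named intent-to-treat, power is given for completers, and the supplied text has no rule for about 17 dropouts per arm, some of whom would leave through the week-8 non-response criterion. Excluding those patients, or censoring them in the time-to-remission analysis, overstates remission.

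With equal 25% dropout, power for the stated primary analysis is about 75% or about 94%, according to what 70/40 mean. The pair is not a bound: on the completer-rate reading, a four-point difference in dropout moves power to 0.83 or 0.66. The plan reports power at 67 per arm under neither reading. The 24-week label is unsupported by the pilot described, though the size of that figure is not refuted and it did not set the sample size.

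**What to change.** 1. Reconcile the remission definition first, because any counting rule depends on it. Section 10.1 item 4.0 uses 6 or less under primary outcomes, but below 6 under naturalistic follow-up, as does the power paragraph. Three consecutive weeks cannot be shown by visits two weeks apart after week 4. Hypothesis 1 calls the outcome responder/remitter status.
2. In the chi-square, analyse all 134 as randomised. Count anyone not documented as remitted on study, including week-8 withdrawals, as a non-remitter. Use the 6-month visits to which non-remitters are invited as a sensitivity analysis, since treatment outside the protocol is offered before them.
3. In the time-to-remission analysis, keep week-8 non-response withdrawals in the risk set as not remitted, at least as a stated sensitivity analysis.
4. Say whether 70/40 are completer or all-patient rates, and restate primary power at 67 per arm on that basis, with a range for unequal dropout.
5. Relabel the figure over 0.9 as a 12-week figure and name the pilot effect used, or delete it.

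The cost is wording in the analysis plan, with no change to enrolment, treatment or visits. The downside is a conditional and possibly less favourable stated power.
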